5.3.5.12 Cases of Accidental Overdose or Medication Error

Accidental overdose and medication error (hereafter collectively referred to as "special situations"), are defined as follows:

- Accidental overdose: accidental administration of a drug in a quantity that is higher than the assigned dose

- Medication error: accidental deviation in the administration of a drug
In some cases, a medication error may be intercepted prior to administration of the drug.

Special situations are not in themselves adverse events, but may result in adverse events. Each adverse event associated with a special situation should be recorded separately on the Adverse Event eCRF. If the associated adverse event fulfills seriousness criteria or qualifies as an adverse event of special interest, the event should be reported to the Sponsor immediately (i.e., no more than 24 hours after learning of the event; see Section 5.4.2). For tiragolumab/placebo and atezolizumab, adverse events associated with special situations should be recorded as described below for each situation:

- Accidental overdose: Enter the adverse event term. Check the "Accidental overdose" and "Medication error" boxes.
- Medication error that does not qualify as an overdose: Enter the adverse event term. Check the "Medication error" box.
- Medication error that qualifies as an overdose: Enter the adverse event term. Check the "Accidental overdose" and "Medication error" boxes.

In addition, all special situations associated with atezolizumab and tiragolumab/placebo, regardless of whether they result in an adverse event, should be recorded on the Adverse Event eCRF as described below:

- Accidental overdose: Enter the drug name and "accidental overdose" as the event term. Check the "Accidental overdose" and "Medication error" boxes.
- Medication error that does not qualify as an overdose: Enter the name of the drug administered and a description of the error (e.g., wrong dose administered, wrong dosing schedule, incorrect route of administration, wrong drug, expired drug administered) as the event term. Check the "Medication error" box.
- Medication error that qualifies as an overdose: Enter the drug name and "accidental overdose" as the event term. Check the "Accidental overdose" and "Medication error" boxes. Enter a description of the error in the additional case details.
- Intercepted medication error: Enter the drug name and "intercepted medication error" as the event term. Check the "Medication error" box. Enter a description of the error in the additional case details.

As an example, an accidental overdose that resulted in a headache would require two entries on the Adverse Event eCRF, one entry to report the accidental overdose and one entry to report the headache. The "Accidental overdose" and "Medication error" boxes would need to be checked for both entries.

5.3.5.13 Patient-Reported Outcome Data

Adverse event reports will not be derived from [REDACTED] or other PRO data by the Sponsor. In addition, the Sponsor will make no attempt to reconcile patient reports of

treatment-related symptoms [REDACTED] with investigator reports of adverse events. Sites are not expected to review the [REDACTED] or other PRO data for adverse events.

5.4 IMMEDIATE REPORTING REQUIREMENTS FROM INVESTIGATOR TO SPONSOR

Certain events require immediate reporting to allow the Sponsor to take appropriate measures to address potential new risks in a clinical trial. The investigator must report such events to the Sponsor immediately; under no circumstances should reporting take place more than 24 hours after the investigator learns of the event. The following is a list of events that the investigator must report to the Sponsor within 24 hours after learning of the event, regardless of relationship to study treatment:

- Serious adverse events (defined in Section 5.2.2; see Section 5.4.2 for details on reporting requirements)
- Adverse events of special interest (defined in Section 5.2.3; see Section 5.4.2 for details on reporting requirements)
- Pregnancies (see Section 5.4.3 for details on reporting requirements)

For serious adverse events and adverse events of special interest, the investigator must report new significant follow-up information to the Sponsor immediately (i.e., no more than 24 hours after becoming aware of the information). New significant information includes the following:

- New signs or symptoms or a change in the diagnosis
- Significant new diagnostic test results
- Change in causality based on new information
- Change in the event's outcome, including recovery
- Additional narrative information on the clinical course of the event

Investigators must also comply with local requirements for reporting serious adverse events to the local health authority and IRB/EC.

5.4.1 Medical Monitors and Emergency Medical Contacts

To ensure the safety of study patients, access to the Medical Monitor is available 24 hours per day, 7 days per week. Details will be provided separately. The Emergency Medical Call Center will connect the investigator with an Emergency Medical Contact, provide medical translation service if necessary, and track all calls. Contact information, including toll-free numbers for the Emergency Medical Call Center, will be distributed to investigators.

5.4.2 Reporting Requirements for Serious Adverse Events and Adverse Events of Special Interest

5.4.2.1 Events That Occur prior to Study Treatment Initiation

After informed consent has been obtained but prior to initiation of study treatment, only serious adverse events caused by a protocol-mandated intervention should be reported. The paper Clinical Trial Serious Adverse Event/Special Situation Reporting Form provided to investigators should be completed and submitted to the Sponsor or its designee immediately (i.e., no more than 24 hours after learning of the event), either by faxing or by scanning and emailing the form using the fax number or email address provided to investigators.

5.4.2.2 Events That Occur after Study Treatment Initiation

After initiation of study treatment, serious adverse events will be reported until [REDACTED] days after the final dose of study treatment [REDACTED]

[REDACTED] In addition, adverse events of special interest will be reported until [REDACTED] days after the final dose of study treatment, regardless of [REDACTED]

[REDACTED] Investigators should record all case details that can be gathered immediately (i.e., within 24 hours after learning of the event) on the Adverse Event eCRF and submit the report via the electronic data capture (EDC) system. A report will be generated and sent to Roche Safety Risk Management by the EDC system.

In the event that the EDC system is unavailable, the paper Clinical Trial Serious Adverse Event/Special Situation Reporting Form provided to investigators should be completed and submitted to the Sponsor or its designee immediately (i.e., no more than 24 hours after learning of the event), either by faxing or by scanning and emailing the form using the fax number or email address provided to investigators. Once the EDC system is available, all information will need to be entered and submitted via the EDC system.

Instructions for reporting serious adverse events that occur after the reporting period are provided in Section [5.6](#).

5.4.3 Reporting Requirements for Pregnancies

5.4.3.1 Pregnancies in Female Patients

Female patients of childbearing potential will be instructed through the Informed Consent Form to immediately inform the investigator if they become pregnant during study treatment or within 5 months after the final dose of atezolizumab or within 90 days after the final dose of tiragolumab/placebo. A paper Clinical Trial Pregnancy Reporting Form should be completed and submitted to the Sponsor or its designee immediately (i.e., no more than 24 hours after learning of the pregnancy), either by faxing or by scanning and emailing the form using the fax number or email address provided to investigators. Pregnancy should not be recorded on the Adverse Event eCRF. The investigator should discontinue study treatment and counsel the patient, discussing the risks of the pregnancy and the possible effects on the fetus. Monitoring of the patient should

continue until conclusion of the pregnancy. Any serious adverse events associated with the pregnancy (e.g., an event in the fetus, an event in the mother during or after the pregnancy, or a congenital anomaly/birth defect in the child) should be reported on the Adverse Event eCRF. In addition, the investigator will submit a Clinical Trial Pregnancy Reporting Form when updated information on the course and outcome of the pregnancy becomes available.

5.4.3.2 Pregnancies in Female Partners of Male Patients

Male patients will be instructed through the Informed Consent Form to immediately inform the investigator if their partner becomes pregnant during treatment with tiragolumab/placebo or within 90 days after the final dose of tiragolumab/placebo. The investigator should report the pregnancy on the paper Clinical Trial Pregnancy Reporting Form and submit the form to the Sponsor or its designee immediately (i.e., no more than 24 hours after learning of the pregnancy), either by faxing or by scanning and emailing the form using the fax number or email address provided to investigators. Attempts should be made to collect and report details of the course and outcome of any pregnancy in the partner of a male patient exposed to study treatment. When permitted by the site, the pregnant partner would need to sign an Authorization for Use and Disclosure of Pregnancy Health Information to allow for follow-up on her pregnancy. If the authorization has been signed, the investigator should submit a Clinical Trial Pregnancy Reporting Form with additional information on the pregnant partner and the course and outcome of the pregnancy as it becomes available. An investigator who is contacted by the male patient or his pregnant partner may provide information on the risks of the pregnancy and the possible effects on the fetus, to support an informed decision in cooperation with the treating physician and/or obstetrician.

5.4.3.3 Abortions

A spontaneous abortion should be classified as a serious adverse event (as the Sponsor considers abortions to be medically significant), recorded on the Adverse Event eCRF, and reported to the Sponsor immediately (i.e., no more than 24 hours after learning of the event; see Section [5.4.2](#)).

If a therapeutic or elective abortion was performed because of an underlying maternal or embryofetal toxicity, the toxicity should be classified as a serious adverse event, recorded on the Adverse Event eCRF, and reported to the Sponsor immediately (i.e., no more than 24 hours after learning of the event; see Section [5.4.2](#)). A therapeutic or elective abortion performed for reasons other than an underlying maternal or embryofetal toxicity is not considered an adverse event.

All abortions should be reported as pregnancy outcomes on the paper Clinical Trial Pregnancy Reporting Form.

5.4.3.4 Congenital Anomalies/Birth Defects

Any congenital anomaly/birth defect in a child born to a female patient exposed to study treatment {or the female partner of a male patient exposed to study treatment} should be classified as a serious adverse event, recorded on the Adverse Event eCRF, and reported to the Sponsor immediately (i.e., no more than 24 hours after learning of the event; see Section 5.4.2).

5.5 FOLLOW-UP OF PATIENTS AFTER ADVERSE EVENTS

5.5.1 Investigator Follow-Up

The investigator should follow each adverse event until the event has resolved to baseline grade or better, the event is assessed as stable by the investigator, the patient is lost to follow-up, or the patient withdraws consent. Every effort should be made to follow all serious adverse events considered to be related to study treatment or trial-related procedures until a final outcome can be reported.

During the study period, resolution of adverse events (with dates) should be documented on the Adverse Event eCRF and in the patient's medical record to facilitate source data verification.

All pregnancies reported during the study should be followed until pregnancy outcome.

5.5.2 Sponsor Follow-Up

For serious adverse events, adverse events of special interest, and pregnancies, the Sponsor or a designee may follow up by telephone, fax, email, and/or a monitoring visit to obtain additional case details and outcome information (e.g., from hospital discharge summaries, consultant reports, autopsy reports) in order to perform an independent medical assessment of the reported case.

5.6 ADVERSE EVENTS THAT OCCUR AFTER THE ADVERSE EVENT REPORTING PERIOD

After the end of the reporting period for serious adverse events and adverse events of special interest (reporting periods defined in Section 5.3.1) all deaths, regardless of cause, should be reported through use of the Long-Term Survival Follow-Up eCRF.

In addition, if the investigator becomes aware of a serious adverse event that is believed to be related to prior exposure to study treatment, the event should be reported through use of the Adverse Event eCRF. However, if the EDC system is not available, the investigator should report these events directly to the Sponsor or its designee, either by faxing or by scanning and emailing the paper Clinical Trial Serious Adverse Event/ Special Situation Reporting Form using the fax number or email address provided to investigators.

5.7 EXPEDITED REPORTING TO HEALTH AUTHORITIES, INVESTIGATORS, INSTITUTIONAL REVIEW BOARDS, AND ETHICS COMMITTEES

The Sponsor will promptly evaluate all serious adverse events and adverse events of special interest against cumulative product experience to identify and expeditiously communicate possible new safety findings to investigators, IRBs, ECs, and applicable health authorities based on applicable legislation.

The Sponsor has a legal responsibility to notify regulatory authorities about the safety of a study treatment under clinical investigation. The Sponsor will comply with regulatory requirements for expedited safety reporting to regulatory authority (which includes the use of applicable systems, such as EudraVigilance), IRBs, ECs, and investigators.

To determine reporting requirements for single adverse event cases, the Sponsor will assess the expectedness of these events through use of the reference safety information in the documents listed below:

Drug	Document
Tiragolumab	Tiragolumab Investigator's Brochure
Atezolizumab	Atezolizumab Investigator's Brochure

The Sponsor will compare the severity of each event and the cumulative event frequency reported for the study with the severity and frequency reported in the applicable reference document.

Reporting requirements will also be based on the investigator's assessment of causality and seriousness, with allowance for upgrading by the Sponsor as needed.

An IMC will monitor the incidence of the above-listed anticipated events during the study. An aggregate report of any clinically relevant imbalances that do not favor the test product will be submitted to health authorities.

6. STATISTICAL CONSIDERATIONS AND ANALYSIS PLAN

This is a Phase II, randomized, double-blind study designed to evaluate the efficacy and safety of atezolizumab plus tiragolumab and atezolizumab plus placebo in approximately 120 patients with metastatic and/or recurrent PD-L1–positive SCCHN.

The analysis of confirmed ORR, PFS, OS, and TTCD will be performed on all randomized patients who receive at least one dose of study treatment. Patients will be grouped based on actual treatment received. DOR will be assessed in patients who have a confirmed objective response.

Safety analyses will be conducted on all randomized patients who receive at least one dose of study treatment. Safety analyses will be performed by treatment arm and will be based on actual treatment received. Specifically, a patient will be included in the atezolizumab plus tiragolumab arm in the safety analyses if the patient receives any amount of tiragolumab, regardless of the initial treatment assignment at randomization.

6.1 DETERMINATION OF SAMPLE SIZE

A total of 120 patients will be enrolled in this study and randomized in a 2:1 ratio (atezolizumab plus tiragolumab and atezolizumab plus placebo). [REDACTED]

[REDACTED]

[REDACTED]

[REDACTED]

6.2 SUMMARIES OF CONDUCT OF STUDY

Enrollment, study drug administration, and discontinuation from the study will be summarized by treatment arm. The reasons for study drug discontinuation will also be tabulated. Major protocol deviations, including major deviations with regard to the inclusion and exclusion criteria, will be summarized by treatment arm.

6.3 SUMMARIES OF DEMOGRAPHIC AND BASELINE CHARACTERISTICS

Demographic and baseline characteristics (including age, sex, race/ethnicity) will be summarized using means, standard deviations, medians, and ranges for continuous variables and proportions for categorical variables, as appropriate. Summaries will be presented overall and by treatment group.

Baseline measurements are the last available data obtained prior to the patient receiving the first dose of any component of study drug, unless otherwise noted.

6.4 EFFICACY ANALYSES

6.4.1 Primary Efficacy Endpoint

The primary efficacy endpoint is confirmed ORR. A confirmed objective response is defined as either a CR or a PR on 2 consecutive occasions ≥ 4 weeks apart, as determined by the investigator using RECIST v1.1. Patients who do not meet these criteria, including patients without any post-baseline tumor assessment, will be considered non-responders. Confirmed ORR is defined as the proportion of patients who had a confirmed objective response.

The primary efficacy analysis will take place once all patients have been enrolled and a

The analysis population for the efficacy analyses will consist of all randomized patients who receive at least one dose of study treatment. Patients will be grouped based on actual treatment received. An estimate of the confirmed ORR and its 95% CI will be calculated using the Wilson score method for each treatment arm.

A sensitivity analysis will be performed for the primary endpoint of confirmed ORR on all randomized patients grouped according to their assigned treatment.

6.4.2 Secondary Efficacy Endpoints

6.4.2.1 Duration of Response

DOR will be assessed in patients who have achieved a confirmed objective response, as determined by the investigator according to RECIST v1.1. DOR is defined as the time interval from the date of the first occurrence of a confirmed objective response until the first date of progressive disease, as determined by the investigator according to RECIST v1.1, or death from any cause, whichever occurs first. Patients who have not progressed and who have not died at the time of analysis will be censored at the time of the last tumor assessment date. Kaplan-Meier methodology will be used to estimate the median DOR for each treatment arm, and Kaplan-Meier curves will be produced. The Brookmeyer-Crowley methodology will be used to construct the 95% CI for the median DOR for each treatment arm (Brookmeyer and Crowley 1982).

6.4.2.2 Progression-Free Survival, Including Progression-Free Survival Rate at 6 Months

PFS is defined as the time between the date of randomization and the date of first documented disease progression, as assessed by investigators according to RECIST v1.1, or death, whichever occurs first. Patients who have not experienced disease progression or have not died by the data cutoff date will be censored at the time of the last tumor assessment. Patients with no post-baseline tumor assessment will be censored at the date of randomization.

Kaplan-Meier methodology will be used to estimate the median PFS for each treatment arm, and Kaplan-Meier curves will be produced. The Brookmeyer-Crowley methodology will be used to construct the 95% CI for the median PFS for each treatment arm (Brookmeyer and Crowley 1982). The PFS rates at 6 months after randomization will be estimated using Kaplan-Meier methodology for each treatment arm, along with 95% CIs calculated using the standard error derived from Greenwood's formula.

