- **Arm A:** Patients will receive atezolizumab at a fixed dose of 1200 mg administered by IV infusion Q3W on Day 1 of each 21-day cycle, followed by tiragolumab at a fixed dose of 600 mg administered to patients by IV infusion Q3W on Day 1 of each 21-day cycle.
- **Arm B:** Patients will receive atezolizumab at a fixed dose of 1200 mg administered by IV infusion Q3W on Day 1 of each 21-day cycle, followed by placebo administered by IV infusion Q3W on Day 1 of each 21-day cycle.

Treatment may be continued as long as patients are experiencing clinical benefit, as assessed by the investigator, in the absence of unacceptable toxicity or symptomatic deterioration attributed to disease progression after an integrated assessment or radiographic data, biopsy results (if available), and clinical status. Patients who meet the criteria for disease progression per RECIST v1.1, but continue to have clinical benefit, will be permitted to continue treatment (atezolizumab plus tiragolumab or atezolizumab plus placebo) if they meet all of the criteria specified in Section 3.1.1 and provide written consent.

Patients will undergo tumor assessments at baseline, every 6 weeks (± 7 days) for the first 30 weeks following Day 1 of Cycle 1, and every 9 weeks (± 7 days) after completion of the Week 30 tumor assessment. Tumor assessments will continue per schedule regardless of treatment delays until radiographic disease progression per RECIST v1.1 or loss of clinical benefit for patients who continue study treatment after radiographic disease progression per RECIST v1.1, withdrawal of consent, death, or study termination by the Sponsor, whichever occurs first. At the investigator's discretion, scans must be performed at any time if progressive disease or loss of clinical benefit is suspected. Radiographic images will be submitted to an independent review facility.

(IRF) for a quality and completeness check, for potential blinded independent central review (BICR), and for temporary storage prior to transferring images to the Sponsor for the long-term retention and eventual secondary or exploratory use.

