Patients who discontinue study treatment (for any reason, including, but not limited to, clinical decline or toxicity) in the absence of radiographic disease progression per RECIST v1.1 will continue scheduled tumor assessments at the frequency described above until radiographic disease progression per RECIST v1.1, withdrawal of consent, death, or study termination by the Sponsor, whichever occurs first, regardless of whether a patient starts a new anti-cancer therapy.

Objective response at a single timepoint will be determined by the investigator according to RECIST v1.1 ([Appendix 4](#)).

In order not to confound the OS endpoint, crossover will not be allowed from Arm B (atezolizumab plus placebo) to Arm A (atezolizumab plus tiragolumab).

Patients will be asked to complete PRO questionnaires during the study treatment and at the study treatment discontinuation visit (see [Appendix 2](#) for PRO schedule).

Serum samples will be collected to monitor atezolizumab and tiragolumab PK and to detect the presence of antibodies to atezolizumab and tiragolumab. [REDACTED]

Safety assessments will include the incidence, nature, and severity of adverse events, and other protocol-specified tests, such as laboratory abnormalities, that are deemed critical to the safety evaluation of the study.

After study treatment discontinuation, survival follow-up information will be collected by means of telephone calls, patient medical records, and/or clinic visits approximately every 3 months until death, loss to follow-up, or study termination by the Sponsor, whichever occurs first (see Section [4.6.1](#)). All patients will be periodically contacted for survival and new anti-cancer therapy information unless the patient requests to be withdrawn from survival follow-up (this request must be documented in the source documents and signed by the investigator). If the patient withdraws from survival follow-up, study staff may use a public information source (e.g., county records) to obtain information about survival status.

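### PFS and DOR count a death as an event however long after the last scan; no visible sensitivity analysis shows how much depends on this, and the PFS censoring text conflicts with the event definition

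*Combined protocol and SAP*

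**What the plan says.** **Event definitions.** PFS runs from randomization to "the date of first documented disease progression, as assessed by investigators according to RECIST v1.1, or death, whichever occurs first" (Section 6.4.2.2). DOR runs from first response to progression "or death from any cause, whichever occurs first" (Section 6.4.2.1). Neither section limits the time between the last scan and the event.

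**Censoring.** For DOR: "Patients who have not progressed and who have not died at the time of analysis will be censored" at the last tumor assessment. For PFS, the corresponding group is defined thus: "have not experienced disease progression or have not died by the data cutoff date will be censored at the time of the last tumor assessment". Section 6.4.2.2 adds: "Patients with no post-baseline tumor assessment will be censored at the date of randomization". It makes no exception for patients who died.

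**Follow-up.** Scans are 6-weekly "for the first 30 weeks following Day 1 of Cycle 1" and 9-weekly "after completion of the Week 30 tumor assessment". They continue after treatment stops, and after new therapy starts, until progression, consent withdrawal, death or the end of the study (Sections 3.1, 4.5.6 and 4.6.1.1). Survival is collected separately, about every 3 months: "All patients will be periodically contacted for survival and new anti-cancer therapy information unless the patient requests to be withdrawn from survival follow-up" (Section 3.1). Public records may be used for patients who withdraw from survival follow-up.

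**Sensitivity analyses.** The only efficacy sensitivity analysis in the visible text concerns confirmed ORR by assigned arm (Section 6.4.1).

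**The concern.** Deaths are found through a channel that does not depend on scanning, so a death can be known long after tumor status ceased to be known. Take two patients last scanned without progression at Week 12 and then lost to imaging. If one dies at month 14, the event definition gives that patient 14 months of PFS. If the other is alive at the cutoff, that patient is censored at Week 12, about 2.8 months. Vital status at the cutoff alone separates them.

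Mandated scanning does not rule out such gaps. Appendix 4 recognizes patients who stop treatment for symptomatic deterioration without objective progression and says this is not an objective response category. Such patients are not PFS events at that point, may well miss later scans, and may die soon.

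At stake are the 6-month PFS rate, the upper part of the PFS and DOR curves, and the comparability of the arms if one loses more patients from scanning. The confirmed ORR is not affected.

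**Working it through.** The documents give no figure for this point, so there is none to reproduce. The check has two parts.

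**1. Wording.** The event definition makes every first death an event; Section 2.1.2 agrees. Two sentences in Section 6.4.2.2 do not fit.
- The PFS censoring sentence joins its conditions with *or*. Read literally, a patient who dies without progression has not progressed and is censored at the last scan. A patient who has progressed but is alive has not died and would be censored too. Only patients with both events would remain as events, which cannot be intended. DOR uses *and*, which is consistent.
- The sentence on patients with no post-baseline scan would censor at randomization a patient who dies before the first scan.

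**2. Size.** Inputs:
- Scan grid: 6 weeks = 1.38 months to Week 30, then 9 weeks = 2.07 months (Section 3.1).
- Median time to progression: 2.6 months (Section 1.7.1) and 5.6 months (Section 1.2.1). These are published PFS medians, used here as an assumption.
- Median OS: 12.3 and 14.9 months (Section 1.2.2), also an assumption for this trial.
- Share assigned to stop scans: not in the documents; 10% assumed, with 5% and 20% as a range. Fewer actually stop, because some progress or die first.
- Stopping: either random (uniform over 0 to 6 months) or informative (0 to 1 month before progression).
- Cutoff per patient: 6 to 24 months, assumed.

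Progression and death times were exponential and independent, with 300,000 simulated patients per scenario. Kaplan-Meier 6-month PFS was computed with nobody stopping scans (R), under the event definition as written (A), and with deaths after two or more missed scans censored at the last scan (B). Results in percent at 10% assigned to stop:

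| Stopping | Median progression / OS (months) | R | A | B | A − R | B − R | Late deaths |
|---|---|---|---|---|---|---|---|
| Random | 2.6 / 12.3 | 16.4 | 17.2 | 16.2 | +0.8 | −0.2 | 2.0 |
| Random | 2.6 / 14.9 | 17.3 | 18.1 | 17.2 | +0.8 | −0.1 | 1.8 |
| Random | 5.6 / 12.3 | 35.9 | 36.2 | 35.4 | +0.3 | −0.5 | 2.4 |
| Random | 5.6 / 14.9 | 38.1 | 38.3 | 37.7 | +0.2 | −0.4 | 2.2 |
| Informative | 2.6 / 12.3 | 16.3 | 19.3 | 17.9 | +3.0 | +1.6 | 3.1 |
| Informative | 2.6 / 14.9 | 17.3 | 20.4 | 19.1 | +3.1 | +1.8 | 2.7 |
| Informative | 5.6 / 12.3 | 35.9 | 38.2 | 37.7 | +2.3 | +1.8 | 2.1 |
| Informative | 5.6 / 14.9 | 38.1 | 40.6 | 40.2 | +2.5 | +2.1 | 1.9 |

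Late deaths are 1.8% to 3.1% of patients: 0.018 × 120 = 2.2 to 0.031 × 120 = 3.7, so about 2 to 4 of 120. Across all scenarios the median time from last scan to such a death was 7.1 to 7.7 months.

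A separate simulation, also with 10% assigned to stop, gave A − R of −0.2 to +0.5 (random, cutoff 6 to 24 months), +0.8 to +1.8 (random, cutoff 24 to 43 months) and +1.9 to +4.2 (stopping just before progression). Together the runs give about 0 to +4 points.

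In the first simulation, A − R was +0.1 to +1.5 points with 5% assigned to stop, and reached +6.3 with 20% informative stopping.

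**Against precision.** Arm sizes are 120 × 2/3 = 80 and 120 × 1/3 = 40. The half-width, ignoring censoring, is 1.96 × √(S(1 − S)/n):
- S = 0.25: 9.5 points (n = 80), 13.4 points (n = 40)
- S = 0.40: 10.7 and 15.2 points
- S = 0.50: 11.0 and 15.5 points

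**The case against.** Counting every death is a common convention. Scans are required after treatment stops and after new therapy, which removes the usual source of gaps; what remains is consent withdrawal and missed visits, at an unknown rate. PFS and DOR are secondary and estimated per arm, with no test in the visible text. All of this stands, and it is why the main rule should stay.

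Four stronger readings are tempting but not supported:
- *Everyone who leaves scanning but stays in survival follow-up is credited with extra time.* Only those who die before the cutoff are. With the 6 to 24 month cutoff, 51% to 62% of scan-stoppers were alive and censored at the last scan. That share falls with longer follow-up.
- *6-month PFS is materially overstated.* With random stopping and an early cutoff the bias is close to zero. The visible text does not give the timing of the primary analysis, so the long-follow-up figures cannot be taken as the expected ones.
- *The written rule and the gap rule bracket the truth.* With informative stopping they do not: in the table, A and B are both above R.
- *The plan plainly credits these deaths.* The definition does, but the PFS censoring sentence read literally does not. The text is in conflict.

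No DOR bias was computed, so nothing is claimed about its size.

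**Conclusion.** The point holds in a limited form. For PFS and DOR, the event definitions place no limit on the gap before a death, the visible text has no analysis showing how much rests on such gaps, and the PFS censoring text contradicts its own event definition.

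The likely effect on the 6-month PFS rate, about 0 to +4 points at 10% assigned to stop, is small beside the CI half-widths. Median PFS was unchanged in most scenarios. Where it moved, under informative stopping, censoring late deaths usually moved it nearly as far (5.52 months as written, 5.51 with late deaths censored, 4.14 with full scanning, at 20% assigned to stop). There the shift comes mainly from lost progression dates rather than from the late-death rule.

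These figures rest on the assumed stopping share, exponential and independent times, borrowed medians and assumed cutoffs. The point is a wording conflict and a missing sensitivity analysis on secondary endpoints; it does not touch the primary analysis.

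**What to change.** 1. Keep death as an event at the death date in the main PFS and DOR analyses.
2. In Section 6.4.2.2, replace *or* with *and* in the censoring sentence, as in DOR. Limit censoring at randomization to patients with no post-baseline scan who have not died.
3. In Sections 6.4.2.1 and 6.4.2.2, pre-specify a sensitivity analysis that censors at the last evaluable scan any progression or death following two or more consecutive missed or not-evaluable scheduled assessments, on the 6-weekly then 9-weekly schedule.
4. Report the number of such events by arm, and both 6-month PFS estimates side by side. Do not describe the two as bounds: the gap rule brings its own informative censoring.

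The cost is a few lines of text, one extra run per endpoint, and a second, usually slightly lower, PFS figure to explain. The counts by arm will show whether the issue matters in this trial. Fixing the rule in advance avoids choosing a gap analysis after seeing the data.
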